6.5.5 Other Safety-Related Assessment

6.5.5.1 Body Weight

Body weight will be summarized using mean, standard deviation, minimum, maximum and median by analysis group and visit. Additionally, a within-subject change will be calculated per visit as the post-baseline measurement minus the baseline measurement (screening visit) and summarized by analysis group.

6.5.5.2 C-SSRS

The results of five questions regarding suicidal ideation, six questions regarding suicidal behavior, suicidal ideation or behavior and self-injurious behavior without suicidal intent will be summarized using number and percent of participants by analysis group at each visit. For

all analysis visits, the data "by the last dose + 7 days" and the data before the first dose date of open label extension part will be included.

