3 OBJECTIVES, ENDPOINTS AND ESTIMANDS

The study objectives and endpoints are outlined in [Table 3].

Objectives	Endpoints	
Primary		
• To assess the dose response of ASP0367 on functional improvement relative to placebo	• Change from baseline in distance walked on the 6MWT at week 24	
• To assess the safety and tolerability of ASP0367 relative to placebo	 Safety and Tolerability through week 24 and end of study: Nature, frequency and severity of TEAEs Vital signs Weight 12-lead ECG Clinical laboratory tests (hematology, biochemistry [including serum cardiac troponin I] and urinalysis) C-SSRS 	
Secondary		
• To assess the dose response of ASP0367 on functional improvement and fatigue relative to placebo	• Change from baseline in Neuro-QoL Short Form Fatigue and Lower Extremity Function (Mobility) scores at week 24	
	• Change from baseline in time spent on the 5XSTS at week 24	
	Change from baseline in MFIS at week 24	
• To assess the effect of ASP0367 in overall	• PGIC scores at week 24	
participant functioning relative to placebo	• Change from baseline in PGIS scores at week 24	

Table 3Study Objectives and Endpoints

Objectives	Endpoints
Exploratory	 
• To assess the pharmacokinetics of ASP0367	 Plasma ASP0367: C_{trough} at weeks 12 and 24 and population pharmacokinetics
• To assess the exposure-response relationship of ASP0367	 Relationship between measured- and model-based pharmacokinetic exposure parameters (e.g., C_{trough}, C_{ave, ss}) of ASP0367 and endpoints of efficacy, safety and pharmacodynamic biomarkers, as appropriate
• To assess the effect of ASP0367 on lower extremity function relative to placebo	• Change from baseline in distance walked on the 6MWT at weeks 4 and 12
	• Change from baseline in minute-by-minute analyses (i.e., 6 th vs 1 st) of 6MWT at weeks 4, 12 and 24
	• Change from baseline in time spent on 5XSTS at weeks 4 and 12
	• Change from baseline in Neuro-QoL Short Form Fatigue score at weeks 4 and 12
	• Change from baseline in Neuro-QoL Short Form Lower Extremity Function (Mobility) score at weeks 4 and 12
	• Change from baseline in MFIS score at weeks 4 and 12
• To assess the effects of ASP0367 on quality	• PGIC scores at weeks 4 and 12
of movement and patient perception of change	• Change from baseline in PGIS scores at weeks 4 and 12
	• Change from baseline in EQ-VAS and EQ-5D-5L index at weeks 4, 12 and 24

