5.4 Primary Safety Endpoints

5.4.1 Treatment Emergent Adverse Events (TEAEs)

AE collection begins after the ICF has been signed and continues until the follow up visit or 28 days after the final IP administration or when the participant is determined to be a screen failure. A TEAE is defined as an AE observed after starting administration of the IP to 28 days after the last dose of IP for double-blind treatment period of the study or moving to the OLE part, whichever comes first.

An IP-related TEAE is defined as any TEAE with a causal relationship of "yes" by the investigator.

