5.4.7 Columbia-Suicide Severity Rating Scale (C-SSRS)

The C-SSRS will be performed by trained site staff via interview at screening, randomization, and all subsequent study visits. At screening, the "Screening" version is to be

used to determine eligibility. During all subsequent visits, the "Since Last Visit" version is used to monitor on study suicidal ideation and behavior after the initial assessment. If possible, continuity of raters should be maintained across visits for each patient. The following five questions regarding suicidal ideation, six questions regarding suicidal behavior and question for non-suicidal self-injurious behavior will be used for analysis.

- Suicidal Ideation ('Yes' to any one of the below 5 questions for suicidal ideation)
 - Wish to be Dead (No/Yes)
 - o Non-Specific Active Suicidal Thoughts (No/Yes)
 - Active Suicidal Ideation with Any Methods (Not Plan) without Intent to Act (No/Yes)
 - o Active Suicidal Ideation with Some Intent to Act, without Specific Plan (No/Yes)
 - o Active Suicidal Ideation with Specific Plan and Intent (No/Yes)
- Suicidal Behavior ('Yes' to any one of the below 5 questions for suicidal behavior)
- Preparatory Acts or Behavior (No/Yes)
 - Aborted Attempt (No/Yes)
 - Interrupted Attempt (No/Yes)
 - Actual Attempt (No/Yes)
 - o Completed Suicide (No/Yes)
- Suicidal Ideation or Behavior ('Yes' to any one of the above 10 questions for suicidal ideation and behavior)
- Self-injurious Behavior Without Suicidal Intent (No/Yes)

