6.8 Additional Conventions

6.8.1 Analysis Windows

Day 1 and Day -1 are defined as the day of start taking the IP and its prior day, respectively.

The following analysis window will be used.

The data summary by visits will be done following the analysis windows specified in the table below:

Analysis Visits	Scheduled Day in	Analysis Windows (day)
	Protocol	
Screening	Day -28	-35 to -14
Week 0 (Baseline)	Day -2 to 1	-2 to 1
Week 1	Day 8	5 to 13
Week 2	Day 14	14 to 18
Week 3	Day 22	19 to 25
Week 4	Day 29	26 to 42
Week 8	Day 57	43 to 70
Week 12	Day 85	71 to 98
Week 16	Day 113	99 to 126
Week 20	Day 141	127 to 154
Week 24	Day 169	155 to 182
Week 28	Day 197	183 to 210
Week 32	Day 225	211 to 238
Week 36	Day 253	239 to 266
Week 40	Day 281	267 to 294
Week 44	Day 309	295 to 322
Week 48	Day 337	323 to 350
Week 52	Day 365	351 to 378
End of Double Blind Part	Day 365	2 to 378
Follow-up	The last dose + 28	The last dose + 28 days to the last dose +
-	days	35 days

For the analyses of safety and efficacy, for all analysis visits excluding follow-up visit, the data "by the last dose + 7 days" and the data before the first dose date of open label extension part will be included.

If more than one observation exists within the analysis window, the observation closest to the scheduled visit day will be selected for that visit. If there are two observations that have the same distance from the scheduled day, the value that is after the scheduled day will be selected in the analysis. If more than one observation is made on the same day, an average value if continuous or the worst value if categorical will be included in the analysis.

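### 52-week SAP 6.5.5.2 and 6.8.1 disagree on whether follow-up C-SSRS data count; read literally, 6.5.5.2 removes them all from the only table with a concurrent placebo group

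*SAP*

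**What the plan says.** Section 6.5.5.2 of the 52-week SAP summarizes the C-SSRS by analysis group at each visit. It then limits the data: for "all analysis visits, the data 'by the last dose + 7 days' and the data before the first dose date" of the OLE part are included. It makes no exception for any visit.

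Section 6.8.1 of the same SAP states the general rule. It opens "For the analyses of safety and efficacy, for all analysis visits excluding follow-up visit" and then gives the same two limits (last dose + 7 days, and before the first OLE dose). Its table lists Follow-up as an analysis visit, with a window that begins "The last dose + 28 days to the last dose" and closes at + 35 days.

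Four other places bear on which rule was meant:

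- SAP section 1 says the plan covers the double-blind part together with its follow-up visit.
- SAP 5.4.7 says the C-SSRS is done "via interview at screening, randomization, and all subsequent study visits", and protocol Table 1 marks it at the follow-up visit.
- Protocol section 3 lists the C-SSRS among the primary safety endpoints, under "Safety and Tolerability through week 24 and end of study".
- Protocol 9.4.3.7 asks for a C-SSRS summary by treatment group and time point and sets no cut-off.

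**The concern.** The C-SSRS sentence repeats the general rule without the words that protect the follow-up visit. A programmer will usually follow the section written for the endpoint. In that case the follow-up C-SSRS is collected and belongs to a primary safety endpoint, but it is left out of the double-blind table. The SAP gives no reason for treating the C-SSRS differently from laboratory tests, vital signs and ECG, which fall under 6.8.1 and keep their follow-up visit.

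At stake is the between-arm view of C-SSRS findings after stopping treatment. The 52-week SAP is the only one of the two plans with a placebo group. The 76-week SAP has two groups, ASP0367 any dose and placebo switched to ASP0367, and neither is a concurrent control. Post-screening visits use the Since Last Visit form, so the follow-up form is the one that covers the interval after the preceding visit.

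**Working it through.** **Inputs**

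- C-SSRS limit: at or before last dose + 7 days, all analysis visits (52-week SAP 6.5.5.2).
- General safety limit: the same + 7 days, follow-up visit exempt (52-week SAP 6.8.1).
- Follow-up window: last dose + 28 to + 35 days (52-week SAP 6.8.1).
- Protocol Table 1: week 24 on Day 169; follow-up on Day 197 with a + 7-day visit window.
- TEAE window: to "28 days after the last dose of IP for double-blind treatment period of the study" or OLE entry, whichever is first (52-week SAP 5.4.1).

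**Step 1: reproduce the follow-up window.** With Day 169 as the reference day, 169 + 28 = 197, the scheduled follow-up day. Adding the 7-day visit window, 197 + 7 = 204 = 169 + 35. This agrees with the SAP's + 28 to + 35.

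**Step 2: overlap with the limit.** The window holds 35 − 28 + 1 = 8 days.

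- Under 6.5.5.2 as written, an assessment on day d after the last dose needs d ≤ 7. No day from 28 to 35 satisfies this: 0 of 8.
- Under 6.8.1 the follow-up visit is exempt: 8 of 8.
- The limit falls 28 − 7 = 21 days before the window opens, so visit-window tolerance cannot bridge it.

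**Step 3: who is affected.** A participant who moves to the OLE has the scheduled follow-up after OLE dosing. That assessment does not belong in a double-blind table, and the OLE limb of both rules removes it properly. The conflict therefore matters only for participants who did not enter the OLE. The documents do not say how many there were.

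**Step 4: where those participants' follow-up C-SSRS goes.**

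| Randomized to | 52-week SAP if 6.5.5.2 governs | 52-week SAP if 6.8.1 governs | 76-week SAP |
|---|---|---|---|
| ASP0367 | excluded | included | included, pooled as any dose |
| Placebo | excluded | included | not in its safety set |

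The last column follows from three parts of the 76-week SAP. Section 4.1 admits placebo participants only if they continued into the OLE, and it expressly leaves out those who discontinued in the double-blind part. Section 6.5.5.2 of that plan sets no C-SSRS limit. Section 6.8.1 of that plan exempts the follow-up visit.

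**Step 5: what the adverse-event route keeps.** TEAEs run to last dose + 28. Suicidality on days + 8 to + 28 (28 − 7 = 21 days) is counted by arm if it is recorded as an adverse event, whichever C-SSRS rule applies.

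**The case against.** The best defence is that 6.5.5.2 is only a shortened restatement of 6.8.1. The wording is nearly the same, 6.8.1 claims to govern safety analyses generally, 6.5.5.2 itself promises a summary at each visit, and the SAP's scope includes the follow-up visit. On that reading nothing is lost. This stands as a possible reading, so exclusion cannot be reported as settled. It does not remove the need to reconcile the text, because the endpoint-specific sentence says something different.

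A second defence is that an on-treatment limit is reasonable. With a half-life of 14.1 to 17.5 hours (protocol 2.2.3.2), 7 days is 168 hours, or 168/17.5 = 9.6 to 168/14.1 = 11.9 half-lives. That supports a + 7-day limit for on-treatment visits, and 6.8.1 uses one. It does not explain dropping the follow-up visit for the C-SSRS alone.

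Third, both documents note that the placebo comparison runs to 24 weeks. That does not settle the matter. Someone whose last dose was on Day 134 has a follow-up window of Days 162 to 169 (134 + 28, 134 + 35), inside 24 weeks, and 6.5.5.2 would still exclude it.

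A reader might also infer more than the documents support:

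- *Post-treatment suicidality is never compared between arms.* It is, for events recorded as adverse events up to + 28 days. Only the C-SSRS follow-up row is at issue.
- *The limit hides the participants taken off treatment for a C-SSRS level of 4 or 5 (protocol 8.1).* The assessment that triggers stopping normally falls on treatment, before the limit, and is already counted.
- *A quarter of post-baseline assessments is lost (weeks 4, 12, 24 and 28).* That schedule is from protocol version 9.0, and SAP section 1 says no participant was evaluated under version 8.0 or later. In this SAP, Week 28 (days 183 to 210) is also a different analysis visit from Follow-up.
- *The difference from the TEAE window is itself an error.* The + 7 limit applies to every visit-based safety summary other than follow-up, so that difference is not specific to the C-SSRS.

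**Conclusion.** The two sections conflict, and the conflict decides whether follow-up C-SSRS data are compared between arms. If 6.5.5.2 overrides 6.8.1, all in-window follow-up C-SSRS assessments (0 of 8 days eligible) drop out of the only C-SSRS table with a concurrent placebo group. If 6.8.1 governs, none do. Exclusion therefore rests on the assumption that the specific section prevails, which is the usual programming convention but is not stated in the SAP.

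The effect is confined to participants who did not enter the OLE, in unknown number. For those on ASP0367 the data still appear, pooled, under the 76-week SAP. For placebo participants who discontinued in the double-blind part they appear in neither plan's C-SSRS table. The practical loss is the comparator. The primary efficacy analysis is untouched. The correction is worth making because it concerns a primary safety endpoint and costs almost nothing.

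**What to change.** In 52-week SAP 6.5.5.2, add the exception for the follow-up visit directly after the reference to all analysis visits, so that the sentence matches 6.8.1. Leave the + 7-day and pre-OLE limits unchanged for the other visits. Then tabulate the C-SSRS by treatment group at the follow-up visit, defined as last dose + 28 to + 35 days and before any OLE dose. If the sponsor does intend to leave the follow-up visit out for the C-SSRS, 6.5.5.2 should say so and give the reason.

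A supplementary count that ends at last dose + 28 days, to mirror the TEAE window, is not a substitute. It would reach only 1 of the 8 follow-up window days (+ 28) and miss + 29 to + 35.

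The cost is one phrase and one row in an existing table. The follow-up C-SSRS is already a scheduled assessment. If the SAP can no longer be revised before database lock, the change can be documented in the clinical study report, as SAP section 1 provides.

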6.6 Other Analyses

Not applicable in this study.

6.7 Interim Analysis

6.7.1 Interim Analysis of Efficacy

The analysis of futility and of efficacy was performed when the first 33 participants completed the efficacy evaluation at week 24 or discontinued as of date the last participant had the week 24 visit, 20-Nov-2023. The change from baseline in distance walked on the 6MWT at week 24 was analyzed using the same MMRM as with the primary endpoint excluding the site group from the model to decide whether the study will continue.

Analysis of Futility

For the futility stop, the study may be stopped if the conditional probability of achieving the criteria below at the final analysis is less than 10%.

Criteria: Lower limit of the 90% CI for the difference is greater than 0 m AND the point estimate of the difference between the ASP0367 75 mg group and the placebo group is greater than 30 m.

In addition to 6MWT at week 24, outputs for participant disposition, demographics and the secondary endpoints 5XSTS, Neuro-QoL Short Form Fatigue score, Neuro-QoL Short Form Lower Extremity Function (Mobility) score, MFIS, PGIC, and PGIS at week 24 were analyzed at the interim analysis.

Analysis of Efficacy

For the efficacy stop, a two-stage group sequential design with Lan-DeMets alpha-spending function determined by means of the O'Brien-Fleming approach was used to preserve the overall two-sided type I error rate of 0.10 between this single interim analysis and the final analysis. If the p-value of the comparison between ASP0367 75 mg and placebo groups at interim analysis is lower than the boundary determined by O'Brien-Fleming approach, efficacy would be considered to be achieved at week 24.

The interim analysis outputs were prepared by an external statistician and presented to the AIDMC who made recommendations about the ongoing conduct of the study. After the AIDMC reviewed the interim analysis results, the AIDMC recommended the study to be stopped because the study met results of the interim analysis the criteria for futility. Details of the analysis were defined in the interim analysis plan.

6.8 Additional Conventions

6.8.1 Analysis Windows

Day 1 and Day -1 are defined as the day of start taking the IP and its prior day, respectively.

The following analysis window will be used.

The data summary by visits will be done following the analysis windows specified in the table below:

Analysis Visits	Scheduled Day in	Analysis Windows (day)
	Protocol	
Screening	Day -28	-35 to -14
Week 0 (Baseline)	Day -2 to 1	-2 to 1
Week 1	Day 8	5 to 13
Week 2	Day 14	14 to 18
Week 3	Day 22	19 to 25
Week 4	Day 29	26 to 42
Week 8	Day 57	43 to 70
Week 12	Day 85	71 to 98
Week 16	Day 113	99 to 126
Week 20	Day 141	127 to 154
Week 24	Day 169	155 to 182
Week 28	Day 197	183 to 210
Week 32	Day 225	211 to 238
Week 36	Day 253	239 to 266
Week 40	Day 281	267 to 294
Week 44	Day 309	295 to 322
Week 48	Day 337	323 to 350
Week 52	Day 365	351 to 378
End of Double Blind Part	Day 365	2 to 378
Follow-up	The last dose + 28	The last dose + 28 days to the last dose +
-	days	35 days

For the analyses of safety and efficacy, for all analysis visits excluding follow-up visit, the data "by the last dose + 7 days" and the data before the first dose date of open label extension part will be included.

If more than one observation exists within the analysis window, the observation closest to the scheduled visit day will be selected for that visit. If there are two observations that have the same distance from the scheduled day, the value that is after the scheduled day will be selected in the analysis. If more than one observation is made on the same day, an average value if continuous or the worst value if categorical will be included in the analysis.

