1.2 Study Schema

Figure 1 Study Level Schema

6MWT: 6-minute walk test; DB: double-blind.

[†] At week 24 while enrollment continues, data from the first approximately 30 evaluable participants will be reviewed in an interim analysis to determine if the futility or efficacy stopping criteria are met while the study is ongoing.

Table 1Schedule of Assessments

Assassments	Screening	Treatment Period										Follow-up
Assessments	Period	Double-blind Treatment (24 weeks)								Period		
Visit Number	V1	V2	V3	V4	V5	V6	V7	V8	V9	V10	V11	V12
Week	-4	0	1	2	3	4	8	12	16	20	24	28
Day	-28	-2 to 1 ^c	8	14	22	29	57	85	113	141	169/EOT_P 2 ^d	197/ EOS ^d
Visit window (days)	-7 to +14	-	± 3	-2 to + 3	± 3	± 3	± 3	± 3	± 3	± 3	± 3	+ 7
Study site visit ^a	Х	Х				X		Х			Х	Х
Follow-up phone call ^b			Х	Х	Х		Х		X	X		
Informed consent	Х											
Medical history	Х											
Demographics	Х											
On-site training for all endpoint assessments	Х											
Verify inclusion/ exclusion criteria	Х	Xe										
Randomization		Х										
Physical examination	Х	Х				Х		Х			Х	Х
Height	Х											
Body weight	Х										Х	Х
Vital signs ^f	Х	Xe				X		Х			Х	Х
Hematology, biochemistry, urinalysis ^g	Х	Х				X		Х			X	Х
Abbreviated biochemistry and hematology ^g			Х	X	Х		Х		Х	Х		
Serology (hepatitis screening)	Х											
Pregnancy test	X ^h	X ^{e,i}				Xi		Xi			Xi	
Table continued on next page												-

Footnotes

- CONFIDENTIAL -

Assessments	Screening	ning Treatment Period									Follow-up Period	
	Period	Double-blind Treatment (24 weeks)										
Visit Number	V1	V2	V3	V4	V5	V6	V 7	V8	V9	V10	V11	V12
Week	-4	0	1	2	3	4	8	12	16	20	24	28
Day	-28	-2 to 1°	8	14	22	29	57	85	113	141	169/EOT_P 2 ^d	197/ EOS ^d
Visit window (days)	-7 to +14	-	± 3	-2 to + 3	± 3	± 3	± 3	± 3	± 3	± 3	± 3	+ 7
Study site visit ^a	Х	Х				Х		Х			Х	Х
Follow-up phone call ^b			Х	Х	Х		Х		Х	Х		
Urine drug and alcohol test	Х											
12-lead ECG ^j	Х	Xe		Х		Х	Х	Х			Х	Х
C-SSRS ^k	Х	Х				Х		Х			Х	Х
6MWT ¹		Х				Х		Х			Х	
5XSTS		Х				Х		Х			Х	
Blood for plasma pharmaco-kinetics ^m		Х						Х			Х	
Serum and urinary biomarkers ⁿ		Х						Х			Х	
Blood for pharmacodynamics (PPARδ target gene expression) ^ο		Х						Х			Х	
Blood sample collection for genotyping		Х										
Blood sample collection for pharmaco-genomics (banking)		Х										
Patient reported outcomes ^p		Х				Х		Х			Х	
Dispense/ Collect IP		Х				Х		Х				
IP dosing		Х	\rightarrow									
Previous and concomitant treatment	Х	Х	Х	Х	Х	Х	Х	Х	Х	Х	Х	Х

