Exercise status ^q	Х	Х	Х	Х	Х	Х	Х	Х	Х	Х	Х	Х
Adverse event assessment	Х	Х	Х	Х	Х	Х	Х	Х	Х	Х	Х	Х

5XSTS: 5 time sit to stand; 6MWT: 6-minute walk test; ALDOA: aldolase A; CK: creatine kinase; C-SSRS: Columbia-Suicide Severity Rating Scale; CYC: cytochrome c; ECG: electrocardiogram; EOS: end of study; EOT_P2: end of treatment during double-blind treatment period; EQ-5D-5L: European Quality of Life 5-dimension, 5-level

24 Jan 2024 *Footnotes* Version 9.0 Substantial Amendment 8

- CONFIDENTIAL -

questionnaire; FLNC: filamin-C; IP: investigational product; MB: isoenzymes found in heart muscle; MFIS: Modified Fatigue Impact Scale; MM: isoenzymes found in skeletal and heart muscle; Neuro-QoL: Quality of Life in Neurological Disorders; PGIC: Patient Global Impression of Change; PGIS: Patient Global Impression of Severity; PPARδ: peroxisome proliferator-activated receptor delta; QTcF: QT interval using Fridericia's correction; WOCBP: women of childbearing potential

- a. All assessments at the study site visit may be performed over 2 to 3 days. Assessments scheduled for each study site visit should be completed within visit window.
- b. The site will perform follow-up phone call visits. Blood sample collection and ECG will be performed by qualified healthcare provider from the home healthcare vendor (ECG will be performed at weeks 2 and 8 only). In case the home healthcare visit is not feasible, the visit can be conducted at the study site.
- c. IP administration should be started after the completion of assessments at week 0, except for postdose blood sampling for pharmacokinetics. The day participants start taking the IP is considered as day 1.
- d. Participants who discontinue the study treatment will visit the site and perform EOT_P2 assessments. Participants will be encouraged to visit the study site for EOT_P2 assessments as soon as the discontinuation of the study treatment. Participants who discontinue the study will be followed until the EOS visit. Participants who remain in the study for efficacy and safety evaluations will continue to follow the schedule of assessments without IP dosing.
- e. To be performed prior to randomization.
- f. Vital signs will be taken prior to blood draw. Blood pressure and pulse will be measured in the sitting or supine position after the participant has rested for at least 5 minutes.

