- g. Safety laboratory will be done by a central laboratory from the screening to EOS. Blood collection for hematology and biochemistry; muscle biomarkers include CK, CK MM, CK-MB and cardiac troponins I and T. Urinary creatinine should be analyzed quantitatively like blood creatinine analysis that will be used for correcting urinary TITIN. Biochemistry and hematology samples will be taken prior to study assessment, except for ECG and vital signs. At follow-up phone call visits, abbreviated biochemistry (including cardiac troponin I) will be collected at the participant's home (abbreviated hematology will only be collected at week 2) by a qualified healthcare provider from the home healthcare vendor. In case the home healthcare visit is not feasible, the visit can be conducted at the study site.
- h. Serum pregnancy tests will be performed for WOCBP.
- i. Urine pregnancy tests will be performed for WOCBP.
- j. ECGs should be performed prior to blood draw. ECGs will be recorded in triplicate (3 separate ECGs with 5-minute resting prior to first ECG and at least 1 minute apart per time point). In addition, ad hoc triplicate ECG may be required to follow up on an elevation of cTnI above the ULN (see Appendix 10.9 for reference range), or when there is an elevation of cTnT above the ULN (see Appendix 10.9 for reference range) or above the participant's baseline value if it was elevated, or when a participant has any signs or symptoms reflecting cardiac involvement, inclusive of new onset shortness of breath. If the QTcF > 450 msec in male participants and > 480 msec in female participants at screening or randomization, one additional triplicate ECG can be performed on the same day in order to determine the participant's eligibility. ECGs at weeks 2 and 8 will be performed at the participant's home by a qualified healthcare provider from the home healthcare vendor. In case the home healthcare visit is not feasible, the visit can be conducted at the study site.
- k. At screening, the "Screening" version is to be used to determine eligibility. During all subsequent visits, the "Since Last Visit" version is used to monitor on-study suicidal ideation and behavior after the initial assessment.
- 1. Following randomization, participants will be encouraged to perform all 6MWTs within a 2-hour window of the performance time recorded during visit 2.

Footnotes continued on next page

- CONFIDENTIAL -

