6.8 Additional Conventions

6.8.1 Analysis Windows

Day 1 and Day -1 are defined as the day of start taking the IP and its prior day, respectively. The following analysis window will be used. The data summary by visits will be done following the analysis windows specified in the table below:

Analysis Visits	Scheduled Day in	Analysis Windows (day)
	Protocol	, , ,
Screening	Day -28	-35 to -14
Week 0	Day -2 to 1	-2 to 1
Week 1	Day 8	5 to 13
Week 2	Day 14	14 to 18
Week 3	Day 22	19 to 25
Week 4	Day 29	26 to 42
Week 8	Day 57	43 to 70
Week 12	Day 85	71 to 98
Week 16	Day 113	99 to 126
Week 20	Day 141	127 to 154
Week 24	Day 169	155 to 182
Week 28	Day 197	183 to 210
Week 32	Day 225	211 to 238
Week 36	Day 253	239 to 266
Week 40	Day 281	267 to 294
Week 44	Day 309	295 to 322
Week 48	Day 337	323 to 350
Week 52	Day 365	351 to 378
Week 56	Day 393	379 to 406
Week 60	Day 421	407 to 434
Week 64	Day 449	435 to 462
Week 68	Day 477	463 to 490
Week 72	Day 505	491 to 518
Week 76	Day 533	519 to 560
End of Treatment	Day 533	2 to 560
Follow-up	The last dose + 28	The last dose + 28 days to the last dose +
_	days	35 days

For all analysis visits excluding follow-up visit, the data "by the last dose + 7 days" will be included.

For participants who received ASP0367 on the double blind part, all analysis visits will be used. For participants received placebo on the double blind part, baseline and analysis visit at and after the first ASP0367 taken will be used.

If more than one observation exists within the analysis window, the observation closest to the scheduled visit day will be selected for that visit. If there are two observations that have the same distance from the scheduled day, the value that is after the scheduled day will be selected in the analysis. If more than one observation is made on the same day, an average value if continuous or the worst value if categorical will be included in the analysis.

For Placebo to ASP0367 group, the measurement at week 52 is used as baseline, and for ASP0367 groups, the measurement at week 0 is used as baseline, unless otherwise specified.

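### Both SAPs put days 12 and 13 in the week-1 analysis window, although Protocol v9.0 allows them for week 2 and they lie nearer day 14 than day 8

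*SAP*

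**What the plan says.** **Visit schedule.** Protocol v9.0 Table 1 (Schedule of Assessments) gives the scheduled days of weeks 1, 2, 3, 4, 8, 12, 16 and 20 as "8 14 22 29 57 85 113 141". The permitted deviations for screening, week 0, week 1 and week 2, in that order, are "Visit window (days) -7 to +14 - ± 3 -2 to + 3". Week 1 is therefore day 8 ± 3, and week 2 is day 14 with 2 days early or 3 days late allowed.

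**Analysis windows.** Section 6.8.1 of the 52-week SAP has "Week 1 Day 8 5 to 13" followed by "Week 2 Day 14 14 to 18". Section 6.8.1 of the 76-week SAP has the same two rows.

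**How the windows are used.** The same section of both SAPs states: "The data summary by visits will be done following the analysis windows specified in the table below". It then sets the selection rule: "If more than one observation exists within the analysis window, the observation closest to the scheduled visit day will be selected for that visit". Assignment therefore follows the study day, not the nominal visit name.

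**What is measured.** Under Protocol v9.0 Table 1, abbreviated biochemistry, which includes cTnI, cTnT, CK and the transaminases (Appendix 6), is drawn at both week 1 and week 2. Of the phone-call visits, "ECG will be performed at weeks 2 and 8 only" (footnote b) and "abbreviated hematology will only be collected at week 2" (footnote g). Week 1 has neither an ECG nor a hematology sample.

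**Where the windows appear in output.** SAP 6.5.2 summarizes laboratory values and changes from baseline at each analysis visit. SAP 6.5.4 does the same for ECG parameters and for the QTcF categories and increases.

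**The concern.** The SAP's cut between week 1 and week 2 does not match the protocol's cut. A week-2 assessment done one or two days early, which v9.0 permits, is treated as a week-1 assessment.

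The effect depends on the type of data. For biochemistry there are then two candidates for the week-1 cell and none for week 2. For ECG and hematology there is no scheduled week-1 value, so the result fills a week-1 cell that should be empty and leaves week 2 blank.

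The stake is the accuracy of the earliest on-treatment safety tables. Under v9.0, week 2 is the first post-baseline ECG and the first post-baseline hematology point. The protocol names heart and skeletal muscle as the target organs (section 2.3.1.1), and safety relative to placebo is a primary objective.

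**Working it through.** **1. Permitted days (Protocol v9.0 Table 1).**
- Week 1: 8 − 3 = 5 to 8 + 3 = 11, so days 5-11.
- Week 2: 14 − 2 = 12 to 14 + 3 = 17, so days 12-17, which is 6 days.

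**2. Overlap with the SAP windows.** SAP week 1 is days 5-13 and SAP week 2 is days 14-18. Of days 12-17, days 12 and 13 fall in the SAP's week 1. That is 2 of 6 permitted days. Days 14-17 are assigned correctly.

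**3. Other visits.** Checking every permitted day for weeks 1, 3, 4, 8, 12, 16, 20 and 24 against its own SAP window shows none outside. Week 2 is the only visit up to week 24 with the mismatch.

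**4. The SAP's own scheduled days, without the protocol windows.**

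| Adjacent visits | Scheduled days | Midpoint | SAP boundary |
|---|---|---|---|
| Weeks 1 and 2 | 8, 14 | 11 | 13/14 |
| Weeks 2 and 3 | 14, 22 | 18 | 18/19 |
| Weeks 3 and 4 | 22, 29 | 25.5 | 25/26 |
| Weeks 4 and 8 | 29, 57 | 43 | 42/43 |
| Weeks 8 and 12 | 57, 85 | 71 | 70/71 |
| Weeks 48 and 52 | 337, 365 | 351 | 350/351 |

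The boundaries between week 12 and week 48 follow the same pattern as the last rows. Only the first boundary is off its midpoint.
- Day 12: 12 − 8 = 4 days from week 1, and 14 − 12 = 2 days from week 2.
- Day 13: 13 − 8 = 5 days from week 1, and 14 − 13 = 1 day from week 2.

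**5. Selection rule for biochemistry.** Take a week-1 draw on any of days 5-11 and a week-2 draw on day 12 or 13. That gives 7 × 2 = 14 combinations, all with both values in the SAP's week-1 window. The week-1 draw is at most 3 days from day 8, and the week-2 draw is 4 or 5 days away. The week-2 draw is selected in 0 of 14 combinations and the tie rule never applies. The participant then has no week-2 biochemistry in the by-visit summary. If there is no week-1 draw in the window, the day-12 or day-13 value is kept but shown as week 1.

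**6. ECG and hematology.** Under v9.0 no week-1 value is scheduled, so a day-12 or day-13 result is shown as week 1 and week 2 is missing.

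**7. After the change.** With week 1 = days 5-11 and week 2 = days 12-18, every permitted day of either visit falls in its own window, and the windows do not overlap.

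**The case against.** The strongest objection concerns the protocol version. The -2 to +3 window is from v9.0. The SAP says that nobody was evaluated under v8.0 or later (section 1) and that all participants took part under v7.0 or earlier (section 5.4.3). The v7.0 windows are not supplied, and the schedule did change: the v9.0 change log moves the week-4 ECG from home to site, and the protocol's extended pharmacokinetic set still refers to week-2 parameters that v9.0 no longer samples.

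This stands as a limit. A reader might infer that visits compliant under the participants' own protocol were misassigned, and the documents do not show that. The statements about which assessments exist at week 1 are likewise v9.0 statements, although the SAP repeats the home ECGs at weeks 2 and 8 and the scheduled day 14. The objection does not remove the point, because step 4 rests only on the SAP's own scheduled days.

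A second objection is that little depends on these cells, and this is largely right. A reader might infer that safety data are lost. They are not:
- The protocol provides for listings of laboratory and ECG data.
- The troponin, amylase, lipase and liver threshold counts use any value in the treatment period (SAP 6.5.2 and 6.5.2.1).
- TEAEs do not depend on visit windows.
- The 6MWT model uses weeks 4, 12 and 24.
- The interim outputs named in SAP 6.7.1 are efficacy, disposition and demographics, so the futility recommendation is not touched.

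Third, a reader might turn 2 of 6 days into a third of the participants. That needs visits spread evenly over days 12-17, which nothing in the documents supports.

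Fourth, the 76-week SAP uses only visits at and after the first ASP0367 dose for participants who switched from placebo. There the cut affects only the ASP0367 any-dose group.

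**Conclusion.** The week-1/week-2 boundary in section 6.8.1 of both SAPs is misplaced. It takes 2 of the 6 week-2 days allowed by Protocol v9.0, and it departs from the approximate-midpoint pattern of the SAP's later boundaries up to week 52.

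The consequence is confined to descriptive by-visit laboratory and ECG/QTcF summaries at weeks 1 and 2. The number of participants affected could be anything from 0 to all. It depends on actual visit dates and cannot be narrowed from the documents.

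The link to permitted visits assumes that the v9.0 window also applied under v7.0 or earlier, which is unverified. The internal inconsistency of the SAP table needs no such assumption. This is a small but definite correction to a stated rule, with no bearing on the efficacy conclusion.

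**What to change.** In the section 6.8.1 table of both SAPs, set week 1 to days 5-11 and week 2 to days 12-18, and leave the other windows unchanged. Confirm the week-2 visit window in the protocol version that participants followed.

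If outputs already exist, count the records dated day 12 or 13, rerun the by-visit laboratory and ECG/QTcF tables, and document the change in the CSR, as section 1 of each SAP provides.

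The cost is two numbers per table, plus any rerun. No test, model or threshold count changes.
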